## 3. Global polyp burden:

During endoscopy, the global polyp burden is estimated by the endoscopist. At a later phase, two independent reviewers will also globally assess polyp burden by viewing both videos per patient, blinded for order. The second video in the pair could take the value of –2 (much better), –1 (better), 0 (same), 1 (worse) or 2 (much worse) relative to the first video. Mean scores are calculated for each subject and averaged for the three reviewers. If the assessment of the reviewers differs by more than 1 point from the assessment of the endoscopist, consensus is needed.

Version number: ,date 24 of 40

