#### 5. TREATMENT OF SUBJECTS

#### 5.1 Investigational product/treatment

Participants will be given sirolimus tablets. The starting dose is 2 mg once daily which will be given in 1mg tablets. On day 7 the first trough level is measured (using the LC-MS/MS method) and if not within the target range of 5-8ng/ml, dosing adjustments are made. In case of dosing adjustments, the next trough level is measured seven days later and this is repeated weekly until the target range is achieved. In case trough levels are within the target range, the next trough level measurement is at month 3, after which dosing adjustments are made if necessary, and at month 6. The maximum daily dose is 40mg. No placebo is given.

We estimate that a total number of 2000 tablets of 1mg are needed: 2 tablets a day for 6 months for 5 patients resulting in approximately 1800 tablets, plus 200 additional tablets in case of loss or if dosing adjustments are needed.

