## 7.1.2. Secondary study parameters/endpoints (if applicable)

- Number of polyps
- Global polyp burden (see definition in chapter 7.2)
- Histology (tubular, tubulovillous or villous histology and degree of dysplasia)
- Patient reported quality of life using HRQoL questionnaires
- Rate of cell proliferation in healthy intestinal mucosa and adenomatous tissue
- Immunohistochemistry of mTOR targets (such as eEF2 kinase, phospho-S6) in healthy intestinal mucosa and adenomatous tissue

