## 1. Size of polyps:

The polyp-size is estimated by the endoscopist using the open biopsy forceps (the most reliable method currently available). Two independent reviewers will also assess polyp size of marked polyps at the LGI endoscopy by viewing matching still images per patient on dual monitors. They are blinded for timing of endoscopy (baseline or follow-up). The mean size per polyp is calculated from the assessments of the three reviewers. If the assessment of the reviewers differs by more than 3mm from the assessment of the endoscopist, consensus is needed.

For the secondary outcome measures, the degree of polyposis will be measured as follows:

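### Global polyp burden averages two blinded reviewers with an endoscopist who knows the timing; the blinded two-reviewer mean should be reported beside it, with its direction decoded first

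*Combined protocol and SAP*

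**What the plan says.** Global polyp burden is a secondary endpoint (sections 2 and 7.1.2) and is defined only in section 7.2, item 3. There are three ratings.

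- The endoscopist: "During endoscopy, the global polyp burden is estimated by the endoscopist".
- The other two raters: "two independent reviewers will also globally assess polyp burden by viewing both videos per patient, blinded for order".

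The scale is relative. "The second video in the pair could take the value of" one of five whole numbers, from -2 at the favourable end to +2 at the unfavourable end, in comparison with the first video. The ratings are then combined: "Mean scores are calculated for each subject and averaged for the three reviewers". Only two reviewers and the endoscopist are named, so the third in that average must be the endoscopist. The last rule is "If the assessment of the reviewers differs by more than 1 point from the assessment of the endoscopist, consensus is needed".

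Section 9.2 adds only that changes in secondary outcomes during follow-up are summarised descriptively. The study has one treated group of five patients; section 5.1 says "No placebo is given".

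**The concern.** The plan takes care to hide timing from the two reviewers, then combines their scores with one from a rater who cannot be blinded to it. In a single-group before-and-after study, knowing that this is the follow-up examination is the same as knowing that the patient has been treated. The endoscopist's rating enters twice: as a third of the mean, and as the yardstick that decides when the blinded scores are reopened. The global score is also an overall impression with no physical reference, whereas polyp size is judged against an open forceps.

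The two-reviewer mean would show whether the combined result depends on the unblinded rating, but the plan does not ask for it. For that mean to be readable, its direction has to be fixed. A reviewer who does not know the order can most naturally score only by position in the pair. Section 7.2 does not say that the score is turned to follow-up versus baseline before averaging or before the 1-point check. It also does not say that the endoscopist's live estimate uses the -2 to +2 scale or compares follow-up with baseline, although the average and the check need both.

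**Working it through.** The plan gives no figure to reproduce for this endpoint. The inputs are the scale (-2 to +2), the three-rater mean and the consensus trigger (gap above 1), all from section 7.2, and the five patients from section 4.4. Let e be the endoscopist's score, r1 and r2 the reviewers' true follow-up-versus-baseline scores, and R = (r1 + r2)/2. I apply the 1-point rule to each reviewer separately.

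**1. Pull of the endoscopist's rating.** Planned mean minus blinded mean = (e + r1 + r2)/3 - R = (e - R)/3.

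- Without a flag, both gaps are at most 1, so |e - R| is at most 1 and the pull is at most 1/3 = 0.33 per patient.
- Example: r1 = r2 = 0 and e = -1. The blinded mean is 0.00, the planned mean is (-1 + 0 + 0)/3 = -0.33, and there is no flag. In all five patients: 5 × (-1/3)/5 = -0.33 for the group.
- Example with a flag: r1 = r2 = 0 and e = -2. The gap is 2 and consensus is needed. The plan does not say how consensus is reached. If it settles anywhere between the raters' own scores (an assumption), the reported value lies between 0 and -2, although both blinded reviewers saw no change.
- The yardstick works the other way too. With r1 = -1, r2 = +1 and e = 0, both gaps are 1 and nothing is flagged, although the blinded reviewers disagree on direction.

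**2. Why decoding comes first.** Suppose the follow-up video is shown first and the score is not decoded. The reviewer's recorded score is then -r, and its gap from the endoscopist is |-r - e| = |e + r|.

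- e and r in the same direction: |e + r| is at least 2, so every such read is flagged. With e = r1 = r2 = -1, the pre-consensus mean is (-1 + 1 + 1)/3 = +0.33 instead of -1.00, with gaps of 2.
- e = 0 and r = ±2: the gap is 2, flagged.
- e = 0 and r = ±1: the gap is 1, not flagged.
- e and r in opposite directions: the gap is 0 or 1, not flagged, and a real disagreement is hidden.

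Take e = 0, r1 = r2 = -1, with both reviewers shown the reverse order:

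| Mean | Decoded | Not decoded | Shift, patient | Shift, five-patient mean |
|---|---|---|---|---|
| Three raters | (0 - 1 - 1)/3 = -0.67 | (0 + 1 + 1)/3 = +0.67 | 4/3 | (4/3)/5 = 0.27 |
| Two reviewers | -1.00 | +1.00 | 2 | 2/5 = 0.40 |

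The two-reviewer mean is therefore the more exposed of the two if decoding is left out.

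**3. Price of the two-reviewer mean.** With equal and independent rater errors, the ratio of standard errors is sqrt((1/2)/(1/3)) = sqrt(1.5) = 1.22.

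**The case against.** The strongest reply is that nothing is hidden or broken. Using the endoscopist's rating is an openly stated choice, and size and number are averaged in the same way. A third rater improves precision. The lack of a placebo does not itself unblind anyone to timing; an endoscopist at the follow-up examination knows the timing in any design. Decoding is ordinary practice: blinding for order presupposes a key, and sections 2 and 9.2 make clear that an effect over follow-up is wanted. The word second may even mean the later examination.

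Most of this stands. The choice is legitimate and the planned mean need not be dropped. The missing placebo matters only because, with no control group, timing and treatment status coincide. None of this is a reason to withhold the blinded result, which costs almost nothing to show.

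A reader might infer something stronger: that the endpoint will carry wrong signs. With order reversed at random in half the patients and a true change of -1, the expected mean would shrink to (-1.00 + 0.33)/2 = -0.33. The documents do not support this. They do not state the display order, and they give no reversal rate or score frequencies. There is no sign error if the order is chronological or the key is applied first. That calculation also ignores consensus, although every reversed pair in it would be flagged.

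**Conclusion.** The point holds as a cheap improvement and is minor. As written, the summary gives a timing-aware rater one third of the weight and the deciding role in consensus. The unflagged pull is at most 0.33 points, per patient or for the group; beyond a 1-point gap, the documents set no limit because the consensus procedure is not described. These are limits of what the rule allows. No bias in the endoscopist's rating is shown, and no expected error is claimed.

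The decoding and scale statements are clarifications. A reversed, undecoded read with a non-zero score escapes the 1-point check only if the endoscopist scored 0 and the reviewer ±1, or if the two truly disagreed on direction.

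The endpoint is secondary and descriptive in five patients, with no test or decision rule attached. Polyp size and number carry no relative score, so the sign question does not arise for them once each value is matched to its examination.

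**What to change.** Add to section 7.2, item 3:

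1. The two blinded reviewers' scores are kept as given before any consensus, and their mean is reported for each patient and for the group beside the planned three-rater mean.
2. The display order is logged for each reviewer and patient. Before any averaging or the 1-point check, a score is multiplied by -1 where the follow-up video was shown first, so that negative always means better at follow-up.
3. The endoscopist's rating compares the follow-up endoscopy with baseline on the same -2 to +2 scale. Follow-up endoscopy is a safer term than 6 months, because section 7.5 provides an earlier sigmoidoscopy for some withdrawn patients.

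The cost is a few sentences, an order log and one recoding step, with no new data. The drawback is the larger rater error of the two-reviewer mean (about 1.22 times under the stated assumptions), which is why the three-rater mean stays in the report.

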#### 7.3 Withdrawal of individual subjects

If they wish to do so, subjects can leave the study at any time for any reason without any consequences. The investigator can decide to withdraw a subject from the study for urgent medical reasons.

#### 7.3.1 Specific criteria for withdrawal

Participants will be withdrawn from treatment under the following circumstances:
-If any of the exclusion criteria apply during the study

## 7.4 Replacement of individual subjects after withdrawal

If participants are withdrawn from the study due to any reason they will not be replaced.

## 7.5 Follow-up of subjects withdrawn from treatment

All participants that have been using sirolimus for at least 1 month and who are withdrawn for any reason, will undergo another sigmoidoscopy within 6 weeks after withdrawal. If patients withdraw due to side-effects of sirolimus, these patients will be contacted by telephone weekly until symptoms have disappeared.

## 7.6 Premature termination of the study

There are no criteria for early termination, as sirolimus has been investigated previously and therefore unknown adverse events (resulting in premature termination of the study) are not to be expected.

Version number: ,date 25 of 40

#### 8. SAFETY REPORTING

## 8.1 Temporary halt for reasons of subject safety

In accordance to section 10, subsection 4, of the WMO, the sponsor will suspend the study if there is sufficient ground that continuation of the study will jeopardise subject health or safety. The sponsor will notify the accredited METC without undue delay of a temporary halt including the reason for such an action. The study will be suspended pending a further positive decision by the accredited METC. The investigator will take care that all subjects are kept informed.

#### 8.2 AEs, SAEs and SUSARs

#### 8.2.1 Adverse events (AEs)

Adverse events are defined as any undesirable experience occurring to a subject during the study, whether or not considered related to the investigational product. All adverse events reported spontaneously by the subject or observed by the investigator or his staff will be recorded.

#### 8.2.2 Serious adverse events (SAEs)

A serious adverse event is any untoward medical occurrence or effect that

- results in death;
- is life threatening (at the time of the event);
- requires hospitalisation or prolongation of existing inpatients' hospitalisation;
- results in persistent or significant disability or incapacity;
- is a congenital anomaly or birth defect; or
- any other important medical event that did not result in any of the outcomes listed above due to medical or surgical intervention but could have been based upon appropriate judgement by the investigator.

An elective hospital admission will not be considered as a serious adverse event.

Subjects will be instructed to contact the investigator to report any symptom and the investigator will question each subject regarding symptoms at the time of each contact moment (at least monthly). All adverse events, including duration and severity, will be captured in the case report forms.

The investigator will report all SAEs to the sponsor without undue delay after obtaining knowledge of the events.

The sponsor will report the SAEs through the web portal *ToetsingOnline* to the accredited METC that approved the protocol, within 7 days of first knowledge for SAEs that result in death or are life threatening followed by a period of maximum of 8 days to complete the initial preliminary report. All other SAEs will be reported within a period of maximum 15 days after the sponsor has first knowledge of the serious adverse events.

#### 8.2.3 Suspected unexpected serious adverse reactions (SUSARs)

Adverse reactions are all untoward and unintended responses to an investigational product related to any dose administered.

Unexpected adverse reactions are SUSARs if the following three conditions are met:

- 1. the event must be serious (see chapter 9.2.2);
- there must be a certain degree of probability that the event is a harmful and an undesirable reaction to the medicinal product under investigation, regardless of the administered dose;
- 3. the adverse reaction must be unexpected, that is to say, the nature and severity of the adverse reaction are not in agreement with the product information as recorded in:
  - Summary of Product Characteristics (SPC) for an authorised medicinal product;
  - Investigator's Brochure for an unauthorised medicinal product.

The sponsor will report expedited the following SUSARs through the web portal *ToetsingOnline* to the METC:

- SUSARs that have arisen in the clinical trial that was assessed by the METC;
- SUSARs that have arisen in other clinical trials of the same sponsor and with the same medicinal product, and that could have consequences for the safety of the subjects involved in the clinical trial that was assessed by the METC.

The remaining SUSARs are recorded in an overview list (line-listing) that will be submitted once every half year to the METC. This line-listing provides an overview of all SUSARs from the study medicine, accompanied by a brief report highlighting the main points of concern.

Version number: ,date 27 of 40

The expedited reporting of SUSARs through the web portal Eudravigilance or ToetsingOnline is sufficient as notification to the competent authority.

The sponsor will report expedited all SUSARs to the competent authorities in other Member States, according to the requirements of the Member States.

The expedited reporting will occur not later than 15 days after the sponsor has first knowledge of the adverse reactions. For fatal or life threatening cases the term will be maximal 7 days for a preliminary report with another 8 days for completion of the report.

## 8.3 Annual safety report

In addition to the expedited reporting of SUSARs, the sponsor will submit, once a year throughout the clinical trial, a safety report to the accredited METC, competent authority, and competent authorities of the concerned Member States.

This safety report consists of:

- a list of all suspected (unexpected or expected) serious adverse reactions, along with an aggregated summary table of all reported serious adverse reactions, ordered by organ system, per study;
- a report concerning the safety of the subjects, consisting of a complete safety analysis and an evaluation of the balance between the efficacy and the harmfulness of the medicine under investigation.

## 8.4 Follow-up of adverse events

All AEs will be followed until they have abated, or until a stable situation has been reached. Depending on the event, follow up may require additional tests or medical procedures as indicated, and/or referral to the general physician or a medical specialist.

SAEs need to be reported till end of study within the Netherlands, as defined in the protocol.

#### 8.5 Safety Committee

All investigators involved in this study (prof. dr. [name], Prof. dr. [name], Dr. [name] and a PhD candidate) are the safety committee. As previously described, safety of this treatment will be monitored by performing regular lab and trough level testing, physical examinations and monthly telephone contacts. All serious and non-serious adverse events that are collected by the PhD candidate will immediately be reported to the safety committee. The

Version number: ,date 28 of 40

safety committee will decide whether it is a serious or non-serious adverse event, the toxicity grade of this event, the relatedness to the study drug and subsequent measures to be taken. This safety committee is needed as sirolimus has not been investigated previously for the indication as being used in this study.

Version number: ,date 29 of 40

#### 9. STATISTICAL ANALYSIS

Descriptive statistics will be used to describe the study population, characteristics and changes in outcome measures during follow-up. SPSS for Windows software (Chicago, IL, USA) version 21.0. will be used for these analysis.

## 9.1 Primary study parameter(s)

Descriptive statistics will be used to describe the changes in outcome measures during follow-up.

## 9.2 Secondary study parameter(s)

Descriptive statistics will be used to describe the changes in outcome measures during follow-up.

## 9.3 Interim analysis (if applicable)

Not applicable.

Version number: ,date 30 of 40

#### 10. ETHICAL CONSIDERATIONS

## 10.1 Regulation statement

The study will be conducted according to the principles of the Declaration of Helsinki (18th WMA General Assembly, Helsinki, Finland, June 1964), which was amended by the 64th WMA General Assembly, October 2013, Fortaleza, Brazil) and in accordance with the Medical Research Involving Human Subjects Act (WMO). The protocol of this study will be submitted to the Medical Ethical Committee of the Academic Medical Center and will not start before formal approval has been granted. All patients are required to sign an informed consent form. The study will also be conducted in accordance with ICH Good Clinical Practice (GCP) and all applicable subject privacy requirements.

#### 10.2 Recruitment and consent

Participants will be given oral and written explanation about the study, before they give written informed consent. Participants will be given as much time as possible to make a decision. Subjects are allowed to withdraw informed consent at any time for any reason if they wish to do so without providing arguments. The results will be published in a peer-reviewed scientific journal. Subjects will be approached for participation by the investigator or colleagues. This invitation could take place at the outpatient clinic or during telephonic contact. Participants will not be compensated for their travel costs.

## 10.3 Compensation for injury

The sponsor/investigator has a liability insurance, which is in accordance with article 7 of the WMO. The sponsor also has an insurance, which is in accordance with the legal requirements in the Netherlands (Article 7 WMO and the Measure regarding Compulsory Insurance for Clinical Research in Humans of 23th June 2003). The insurance applies to the damage that becomes apparent during the study or within 4 years after the end of the study:

- € 650.000,-- (i.e. six hundred and fifty thousand Euro) for death or injury for each subject who participates in the Research;
- 2. € 5.000.000,-- (i.e. five million Euro) for death or injury for all subjects who participate in the Research;
- 3. € 7.500.000,-- (i.e. seven million five hundred thousand Euro) for the total damage incurred by the organisation for all damage disclosed by scientific research for the Sponsor as 'verrichter' in the meaning of said Act in each year of insurance coverage.

The insurance applies to the damage that becomes apparent during the study or within 4 years after the end of the study.

## 10.4 Incentives (if applicable)

Participants will not receive any reimbursements.

Version number: ,date 32 of 40

### ADMINISTRATIVE ASPECTS, MONITORING AND PUBLICATION

## 10.5 Handling and storage of data and documents

Endoscopically collected material of adenomatous tissue, as part of routine care, will be stored according to regulations of the department of pathology in the AMC. Slides of this adenomatous tissue, used for the assessment of immunohistochemistry and cell proliferation rates, and endoscopically collected material of healthy intestinal mucosa, will be analysed and stored at the Tytgat institute. Source documents and CRFs will be stored by the project leader for 15 years after closure of the trial. Data of the subjects will be coded in order of participation. The code and the data are stored in different locations. The code can only be seen by the investigators. Qualified authorities can get insight in the code and data, but only when accompanied by the investigators. Informed consent forms are kept in separate files, to ensure the data security. The handling of personal data will comply with the Dutch Personal Data Protection Act (in Dutch: De Wet Bescherming Persoonsgegevens, Wbp).

#### 10.6 Monitoring and Quality Assurance

Not applicable.

#### 10.7 Amendments

A 'substantial amendment' is defined as an amendment to the terms of the METC application, or to the protocol or any other supporting documentation, that is likely to affect to a significant degree:

- the safety or physical or mental integrity of the subjects of the trial;
- the scientific value of the trial;
- the conduct or management of the trial; or
- the quality or safety of any intervention used in the trial.

All substantial amendments will be notified to the METC and to the competent authority.

Non-substantial amendments will not be notified to the accredited METC and the competent authority, but will be recorded and filed by the sponsor.

Version number: ,date 33 of 40

